[Part 3 of 9 of the document. The other parts are not shown.]

Data collection on the eCRF must follow the instructions described in the CRF Completion Guidelines. The investigator has ultimate responsibility for the collection and reporting of all clinical data entered on the eCRF. The investigator or designee as identified on Form FDA 1572 (where applicable) must sign the completed eCRF to attest to its accuracy, authenticity, and completeness.

Completed, original eCRFs are the sole property of Eisai and should not be made available in any form to third parties without written permission from Eisai, except for authorized representatives of Eisai or appropriate regulatory authorities.

9.6.2 Clinical Data Management

All software applications used in the collection of data will be properly validated following standard computer system validation that is compliant with all regulatory requirements. All data, both eCRF and external data (eg, laboratory data), will be entered into a clinical system.

Electronic source (eSource) methodology may be used for some of the clinical efficacy and HRQoL assessments performed in this study.

9.7 Statistical Methods

All statistical analyses will be performed by the sponsor or designee. Statistical analyses will be performed using SAS software or other validated statistical software as required.

All statistical tests will be based on the 5% (2-sided) level of significance, unless specified.

9.7.1 Statistical and Analytical Plans

All statistical analyses will be performed by the Sponsor or designee after the study is completed and the database is locked and released for unblinding.

9.7.1.1 Study Endpoints

9.7.1.1.1 PRIMARY ENDPOINT

The primary endpoint of the study is:

- Change from baseline in the CDR-SB at 24 months.

9.7.1.1.2 SECONDARY ENDPOINTS

The secondary endpoints of the study are:

- Time to worsening of CDR scores by 24 months (eg, the worsening of global CDR score is defined as an increase from baseline by at least 0.5 points on the global CDR scale on 2 consecutive scheduled visits at which global CDR is undertaken)
- Time to conversion to dementia for subjects who were not clinically staged as dementia at Baseline based on clinical diagnosis
- The rate of change over time (mean slope) based on CDR-SB score over 24 months
- Change from baseline in CDR-SB at 27 months (ie, 24 months of treatment plus 3 months posttreatment follow-up) (revised per Amendment 01)
- Change from baseline in ADAS-cog₁₄, MMSE, and FAQ at 24 months
- Change from baseline in ADAS-cog₁₄ Word List (immediate recall and delayed recall) at 24 months (revised per Amendment 01)

9.7.1.1.3 EXPLORATORY ENDPOINTS

The exploratory endpoints of the study are:

- Time to change of concomitant AD treatment (ie, dose increase and/or initiation of treatment with AChEI or memantine after randomization) by 24 months
- The proportion of subjects at 24 months who received dose increases and/or initiation of treatment with AChEI or memantine after randomization
- The rate of change over time (mean slope) based on NPI-10 item score over 24 months
- Change from baseline in NPI-10 item at 24 months
- Change from baseline in EQ-5D (subject self-reported, study partner self-reported, and subject measured by proxy) and QOL-AD (subject and study partner) at 24 months
- Change from baseline in Zarit's Burden Interview at 24 months

9.7.1.1.4 BIOMARKERS ENDPOINTS

The biomarker endpoints for this study are:

- Change from baseline in amyloid PET SUVR composite at 24 months for brain amyloid levels
- Change from baseline in tau PET signal at 24 months (revised per Amendment 05)
- Change from baseline in CSF biomarkers t-tau and p-tau at 24 months
- Change from baseline in CSF amyloid biomarkers A β (1-42), and A β (1-x) at 24 months (revised per Amendment 04)
- Change from baseline in total hippocampal volume at 24 months using vMRI (revised per Amendment 01)
- Change from baseline in the preservation of connectivity on fMRI at 24 months

9.7.1.2 Definitions of Analysis Sets

- The Randomized Set is the group of subjects who are randomized to study drug.
- The Safety Analysis Set is the group of subjects who receive at least 1 dose of study drug and have at least 1 postdose safety assessment.
- The Full Analysis Set (FAS) is the group of randomized subjects who receive at least 1 dose of study drug and have baseline and at least 1 postdose primary efficacy measurement.
- The Per Protocol Analysis Set (PPS) is the subset of subjects in the FAS who sufficiently comply with the protocol. The PP Analysis Set will be used to conduct a

sensitivity analysis of the primary efficacy endpoint. Details of the evaluability criteria will be determined before database lock and treatment unblinding, and will be specified in the statistical analysis plan.

- The PK Analysis Set is the group of subjects with at least 1 quantifiable elenbecestat (E2609) plasma concentration with a documented dosing history.
- The PD Analysis Set is the group of subjects who have sufficient PD data to derive at least 1 PD parameter.

9.7.1.3 Subject Disposition

The number of subjects screened, the number (percent) of subjects who failed screening, and the reasons for screen failure will be summarized, based on data reported on the Screening Disposition eCRF. The distribution of the number of randomized subjects enrolled by each site will be summarized for each randomized treatment group. The primary reasons for screen failures (did not meet inclusion or met exclusion criteria, AE, lost to follow-up, withdrawal of consent, and other) will be presented.

Study Completion: the number (percent) of randomized and treated subjects who completed the study and who discontinued from the study will be summarized according to the primary reason for discontinuation and secondary reason(s) for discontinuation, based on data reported on the Subject Disposition (Study Phase) CRF. The number (percent) will be presented by treatment group and total for subjects; randomized, not treated, treated, who completed the study, and discontinued from the study. The primary reasons for early withdrawal from the study are: AE, lost to follow-up, subject choice, withdrawal of consent, pregnancy, study terminated by sponsor, and other. The secondary reasons for early withdrawal from the study are: AE, subject choice, and other.

Completion of Study Treatment: the number (percent) of randomized and treated subjects who completed study drug and who discontinued from study drug will be summarized according to the primary reason for discontinuation and also according to secondary reason(s) for discontinuation, based on data reported on both the Subject Disposition (Study Phase) eCRF and ED from Study Drug eCRF. The number (percent) will be presented by treatment group and total for subjects; randomized, not treated, treated, who completed study drug, and discontinued from study drug. The primary reasons for early discontinuation from the study drug are: AE, subject choice, pregnancy, inadequate therapeutic effect, and other. The secondary reasons for early discontinuation from the study drug are: AE, subject choice, inadequate therapeutic effect, and other.

9.7.1.4 Demographic and Other Baseline Characteristics

Demographic and other baseline characteristics for the Safety Analysis Set and FAS will be summarized for each treatment group using descriptive statistics. Continuous demographic and baseline variables include age, CDR scores, ADAS-cog₁₄, MMSE and FAQ; categorical variables include sex, age group (equal or less than 65 years, age greater than 65 years), race, ethnicity, region, *ApoE4* genotype, prior treatment with AChEIs or memantine (no or yes),

and clinical subpopulation (MCI due to AD or the early stages of mild AD). (revised per Amendment 01)

9.7.1.5 Prior and Concomitant Therapy

All investigator terms for medications recorded in the eCRF will be coded to an 11-digit code using the World Health Organization Drug Dictionary (WHO DD) (Mar 2014). The number (percentage) of subjects who took prior and concomitant medications will be summarized on the Safety Analysis Set by treatment group, Anatomical Therapeutic Chemical class, and WHO DD preferred term (PT). Prior medications will be defined as medications that stopped before the first dose of study drug. Concomitant medications will be defined as medications that (1) started before the first dose of study drug and were continuing at the time of the first dose of study drug, or (2) started on or after the date of the first dose of study drug up to the date of the last dose. All medications will be presented in subject data listings.

Medications taken within the 12-week Follow-Up Period will also be recorded.

9.7.1.6 Efficacy Analyses

The FAS will be used as the primary population for all efficacy analyses, while the PPS will be used as the supportive population.

9.7.1.6.1 PRIMARY EFFICACY ANALYSIS

The primary analysis will be based on an intent to treat philosophy without regard to adherence to treatment. The primary analysis of the change from baseline in CDR-SB at 24 months will be performed to compare elenbecestat (E2609) 50 mg per day versus placebo using a linear mixed effects model for repeated measures (MMRM) on the FAS. The MMRM model will include baseline CDR-SB as a covariate, with treatment group, visit, randomization stratification variables (ie, region [7 levels], clinical dementia [yes, no], and concurrent AD medication use at randomization (Visit 2) [yes, no]), and treatment group-by-visit interaction as fixed effects. (revised per Amendments 01 and 02) An unstructured covariance matrix will be employed to model the covariance of within subject effect; if MMRM fails to converge then a covariance structure with fewer parameters from the following list will be employed according to the prespecified order in the list until the MMRM converges. The list of covariance structure will include Heterogeneous Toeplitz, Toeplitz, Heterogeneous Compound Symmetry, and Compound Symmetry. This primary analysis will include all observed post baseline data of the change from baseline in CDR-SB without imputation of missing values. The treatment effect for elenbecestat (E2609) versus placebo will be compared at 24 months based on MMRM model. The LS means and difference in LS means between elenbecestat (E2609) treatment group and placebo, and corresponding 95% CI will be presented.

The null hypothesis is that there is no difference in the mean change from baseline in CDR-SB at 24 months between elenbecestat (E2609) 50 mg per day and placebo. The corresponding alternative hypothesis is that there is a difference in the mean change from baseline in CDR-SB at 24 months between elenbecestat (E2609) 50 mg per day and placebo.

The primary analysis will be repeated to minimize the impact of change in concomitant AD medications where efficacy data after initiation of new AD medications and increase of current AD medications will be censored.

The following sensitivity analysis will be conducted to evaluate the impact of missing data: the primary endpoint will be analyzed using ANCOVA after multiple imputation. The ANCOVA model will include baseline CDR-SB as a covariate, with treatment group and randomization stratification variables as factors.

Subgroup analysis (eg, *ApoE4* genotype) and additional sensitivity analysis for the primary endpoint will be performed as appropriate. (revised per Amendment 01)

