9.7.1.8.5 OTHER SAFETY ANALYSES

Cognitive decline will be assessed as a safety assessment, in addition to efficacy assessments. Cognitive assessments will include the ADAS-cog₁₄, MMSE, and CDR. (see [Section 9.7.1.6](#)).

vMRI will be used to evaluate disease modification as indicated by measurements of brain atrophy, including the change from Baseline in terms of the measured hippocampal volume based upon the centralized measurement of the structure on repeated MRIs. A large number of studies, including the AD Neuroimaging Initiative, have shown that quantitative measurements of hippocampal, whole brain, and total ventricular volume provide robust and reliable biomarkers of disease progression, and potential for assessment of PD efficacy.

MRI sequences will be collected for all subjects at 12 and 24 months per the Schedule of Assessments. vMRI data will be analyzed at the Screening Visit and at Visits 9 and 13 (12 and 24 months of treatment). QC and normalization procedures for measurements of the whole brain, total ventricular volume, and right and left hippocampal volumes will be based on a validated algorithm and conducted in the same central laboratory. Additional analysis of regions of interest and cortical thickness may also be performed.

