9.7.2 Determination of Sample Size

The sample size for this study is estimated based on comparison of elenbecestat (E2609) versus placebo with respect to the primary efficacy endpoint, the change from baseline CDR-SB at 24 months. Based on available ADNI data [amyloid positive, MMSE equal or greater than 24, late MCI (global CDR=0.5) populations from ADNI, ADNI 2 and ADNI GO] the mean and the standard deviation of the change from baseline in the CDR-SB at 24 months in the placebo group are assumed to be 1.75 and 2.05, respectively. Therefore, assuming a 25% reduction in the mean change from baseline CDR-SB at 24 months for the elenbecestat

(E2609) 50 mg per day dose group compared to placebo with a common standard deviation of 2.05 and an estimated 30% dropout rate in this study, a total sample size of 1330 subjects, 665 subjects in each treatment group, will be required to detect the treatment difference between elenbecestat (E2609) 50 mg per day and placebo using a 2-sample t-test with 90% power at a significance level of 2-sided alpha =0.05.

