Subject demography and medical history will be obtained before completing the following cognitive/clinical assessments: MMSE, International Shopping List Task (ISLT), CDR, and the modified Hachinski ischemic scale. (revised per Amendment 01) The Cogstate Brief Battery (CBB) will be administered in the 20 to 30 minutes between the ISLT total recall and delayed recall tests as a common distractor task. It is recommended that the MMSE and ISLT be completed, and eligibility on these assessments confirmed, prior to the CDR being administered. Subjects who are considered ineligible for the study based on these assessments should not continue with the rest of the Tier 1 assessments. For any given subject, every effort should be made to ensure that the CDR rater remains unchanged throughout the study. (revised per Amendment 04)

All subjects will be confirmed as meeting the diagnostic criteria for either MCI due to AD or the early stages of mild AD, and that they do not have other medical conditions which may interfere with study participation. The diagnosis and clinical disease staging will be verified via a central review process, and adjudicated if necessary (adjudication will only occur when there is a discrepancy between the diagnosis and clinical disease staging made by the site compared to that determined by the central review process; moreover, where adjudication is required, it will be undertaken by an independent assessor(s)). Confirmation of the diagnosis and clinical disease staging by central review will not be required in order for the subject to progress to Tier 2 of the Screening Visit, but will be required before the subject progresses to Tier 4. (revised per Amendment 04)

9.1.1.1.2 TIER 2

Tier 2 assessments may be started and/or completed on the same day as Tier 1 assessments, but only after all Tier 1 assessments have been completed and eligibility to continue confirmed. Tier 2 assessments comprise the Columbia Suicide Severity Rating Scale (C-SSRS), and the following quality of life assessments: (revised per Amendment 01)

- EQ-5D: There are 3 separate administrations of the EQ-5D as follows (revised per Amendment 02): (1) in the subject by self report, (2) in the study partner by self report, (3) in the subject by proxy using the study partner

- QOL-AD: There are 2 separate administrations of the QOL-AD as follows (revised per Amendment 02): (1) in the subject by self report, (2) in the subject by proxy using the study partner

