- Zarit's Burden Interview: this is an assessment of the study partner.

The quality of life assessments conducted at Screening Visit 1, Tier 2 will act as the baseline measures for the study.

9.1.1.1.3 TIER 3

Tier 3 assessments may be started and/or completed on the same day as Tier 2 assessments, but only after all Tier 2 assessments have been completed and eligibility to continue confirmed. Tier 3 assessments include a complete physical examination with dermatologic review, a full neurologic exam, measurement of vital signs (body temperature, sitting heart rate, and sitting BP), measurement of height and weight, and a single 12-lead ECG. Blood samples will be taken for measures of clinical chemistry, hematology, thyroid function, vitamin B12, and for a viral screen. Blood samples will also be taken for pharmacogenomic (PGx) analyses, AD diagnostic/exploratory biomarkers, and for immunologic assessments. (revised per Amendment 04) Some of the immunologic assessment blood sample will be used to prepare isolated peripheral blood mononuclear cells (PBMCs), which will be stored for testing and/or evaluation of lymphocyte subsets as required. (revised per Amendments 03 and 04) The results of some of the immunologic assessments will be provided to the DSMB for periodic review during the study. (revised per Amendment 01) A urine sample will also be taken in order for urinalysis to be conducted. Finally, a serum pregnancy test will be conducted for females of child-bearing potential.

9.1.1.1.4 TIER 4

Tier 4 may only be started following the confirmation of eligibility from the results of the assessments performed in all of the preceding tiers of screening. Tier 4 comprises an MRI scan for brain abnormalities which may exclude study participation. Additional scanning sequences for vMRI and fMRI assessments will be run immediately following the eligibility MRI sequences in all subjects. The MRI assessments conducted during Screening will also be used as the baseline MRI assessments for the respective measures. Results of the Screening MRI will be valid for 90 days from the date of scanning. The MRI will not need to be repeated should the subject be randomized within that time period either under their original subject identification number or under a new re-screening subject identification number. (revised per Amendment 04)

9.1.1.1.5 TIER 5

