9.1.2.1 Treatment Period

During Visit 2, the following assessments will be completed before the subject receives their first dose of study drug: MMSE, CDR, ADAS-cog₁₄, FAQ, and NPI-10. (revised per Amendment 01) These assessments will provide baseline measurements for the study. For any given subject, every effort should be made to ensure that the CDR rater remains unchanged throughout the study. (revised per Amendment 04) Inclusion and exclusion

criteria will again be reviewed together with concomitant medications and assessment of AEs. A single 12-lead ECG will be conducted. All ECG recordings will be evaluated by a central reader. (revised per Amendment 01) The Columbia-Suicide Severity Rating Scale (C-SSRS) will also be administered. A baseline routine physical examination with dermatologic review, vital signs measurements, clinical laboratory testing (including viral characterization), urinalysis using urine dipstick, and a urine pregnancy test (females of child-bearing potential only), will be performed. Additional blood samples will be taken for PD/exploratory biomarkers and immunologic assessments. (revised per Amendment 04) Some of the immunologic assessment blood sample will be used to prepare isolated peripheral blood mononuclear cells (PBMCs) which will be stored for testing as required. (revised per Amendment 03) The results of some of the immunologic assessments will be provided to the DSMB for periodic review during the study. (revised per Amendment 01) Whilst there is no prescribed order in which the assessments at each visit are to be performed, the subject component of the cognitive, functional and quality of life assessments are to be performed in the morning whenever possible, or consistently at the same time of the day and ideally should be completed before the more invasive procedures (eg, physical examination, ECG, blood draw).

Subjects will be randomized at Visit 2 (Day 1) to receive elenbecestat (E2609) 50 mg per day or placebo administered orally QD in the morning with or without food. Subjects will be encouraged to stay at the site for observation for at least 30 minutes following their first dose of study drug. The duration of this observation period can be extended at the Investigator's discretion, eg, if warranted by medical history or concomitant medication. (revised per Amendment 04) Double-blinding to study drug will be in effect throughout the Treatment Period.

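### The primary model leaves out baseline ADAS-cog14, which is scheduled for every subject before the first dose; this forgoes some precision at month 24 but is not an error

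*Protocol*

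**What the plan says.** Section 9.7.1.6.1 sets out the primary MMRM: "The MMRM model will include baseline CDR-SB as a covariate, with treatment group, visit, randomization stratification variables" (region, clinical dementia, concurrent AD medication) and treatment-by-visit. The sensitivity ANCOVA after multiple imputation uses baseline CDR-SB, treatment and the same strata. Neither model has a clause allowing further terms. The ANCOVA relating clinical to biomarker changes in 9.7.1.6.2 does have one.

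Section 9.1.2.1 schedules MMSE, CDR, ADAS-cog14, FAQ and NPI-10 at Visit 2 before the first dose and states: "These assessments will provide baseline measurements for the study". Section 9.7.1.4 lists ADAS-cog14 among the baseline variables, but only to be summarised.

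Two other pre-dose measures exist for every subject. Screening Tier 1 comprises "MMSE, International Shopping List Task (ISLT), CDR, and the modified Hachinski ischemic scale", so a CDR precedes the Visit 2 CDR. Tier 4 adds volumetric MRI: "The MRI assessments conducted during Screening will also be used as the baseline MRI assessments for the respective measures".

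**The concern.** A prespecified baseline covariate that predicts the outcome lowers the residual variance of a randomised comparison without affecting its type I error. Here one severity score and a dementia yes/no stratum carry all the adjustment for disease stage. A second, directly tested cognitive score is collected anyway and goes unused. The month 24 contrast is the single test that decides the trial, and under 9.7.1.6.2 secondary testing proceeds only if it is significant, so any avoidable variance in its standard error matters there first. The protocol also warns in 9.7.3 that the trial SD may exceed the ADNI value used for planning, which makes spare precision more useful.

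**Working it through.** **Inputs (section 9.7.2).** Placebo mean change and SD "in the placebo group are assumed to be 1.75 and 2.05, respectively"; effect from "assuming a 25% reduction in the mean change from baseline CDR-SB at 24 months"; "2-sample t-test with 90% power at a significance level of 2-sided alpha =0.05"; 30% dropout; 665 per arm.

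**The plan's own figure.**
- Difference: 0.25 × 1.75 = 0.4375.
- Normal formula: n = 2 × (1.960 + 1.282)² × 2.05² / 0.4375² gives 462 evaluable per arm; 462 / 0.70 = 660, total 1320.
- Exact noncentral t: 463 per arm; 463 / 0.70 rounds up to 662, total 1324.
- The stated 1330 is reproduced within 1%. With 665 × 0.70 = 465.5 evaluable per arm, power is 90.2%.

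**Adding a covariate.** Let R² be the further share of the variance of the 24-month change that the covariate explains. Then residual SD = 2.05 × √(1 − R²), SE = residual SD × √(2/465.5), and the equivalent extra randomised subjects are 1330 × (1/(1 − R²) − 1). R² is assumed.

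| R² (assumed) | Residual SD | SE | Power (noncentral t) | Equivalent extra subjects |
|---|---|---|---|---|
| 0 | 2.050 | 0.134 | 90.2% | 0 |
| 3% | 2.019 | 0.132 | 91.0% | 41 |
| 5% | 1.998 | 0.131 | 91.6% | 70 |
| 10% | 1.945 | 0.128 | 92.9% | 148 |

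**When these gains are reached.** The table assumes that the covariate removes its full share of month 24 variance. An ANCOVA at month 24 does this with a main effect. In an MMRM over all visits, a main effect imposes one coefficient on every visit, whereas a predictor of decline has an effect that grows with time.

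This was checked with an assumed model: eight quarterly visits (months 3 to 24, the CDR visits on treatment in Table 4), complete data, random slopes, month 24 SD 2.05 and visit-noise SD 0.5 to 1.0. With a main effect only:
- Effect growing linearly from zero: a nominal R² of 10% delivers about 1% to 4% (power 90.5% to 91.2%), and a nominal 5% delivers about 0.5% to 1.8% (power 90.3% to 90.7%).
- 30% of the month 24 effect already present at baseline: a nominal 10% delivers about 6% to 7% (power up to about 92.1%).

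With a covariate-by-visit term the month 24 coefficient is free and the table applies. The cost is one parameter per visit, eight through month 24, against 2 × 465.5 = 931 evaluable subjects.

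**The case against.** The strongest reply is that nothing here is wrong. Baseline outcome plus the stratification factors is a conventional covariate set, the test is unbiased, and 90% power is met without more. Because 2.05 is an unadjusted SD, the planned MMRM probably has somewhat more than 90.2% power already. ADAS-cog14, CDR-SB and the dementia stratum also overlap, so the added R² may lie at the low end. All of this stands, and it limits the point to forgone precision.

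Three stronger readings are tempting and are not supported:

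- *Baseline CDR-SB is a weak predictor because entry requires a global CDR of 0.5.* The protocol gives no baseline SD for CDR-SB and no correlation with decline. The criterion restricts the global score, not the sum of boxes. It allows a memory box of 0.5 or more, and up to about 25% of subjects may have mild dementia.
- *Hippocampal volume belongs in the model because the protocol calls it a marker of progression.* Section 9.7.1.8.5 says "quantitative measurements of hippocampal, whole brain, and total ventricular volume provide robust and reliable biomarkers of disease progression", but the sentence before it concerns change on repeated MRIs. That supports volume as a tracker of change; it does not show that one screening volume predicts CDR-SB decline. Section 9.5.1.3.2 also allows 1.5T or 3T and several scanner types, so a raw volume would mix head size and scanner differences with disease.
- *Any added main effect would earn the full tabulated gain.* The growing-effect check shows otherwise for the MMRM.

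Screening CDR-SB is the same instrument as the Visit 2 baseline, ideally with the same rater, and normally at most 50 to 80 days earlier. Its benefit would come from averaging measurement error, which the protocol does not quantify.

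**Conclusion.** The point holds as a low-cost improvement, not as a defect. The primary MMRM and the imputation ANCOVA omit a baseline cognitive score scheduled for every subject. If that score explains a further 3% to 10% of the month 24 variance, power rises by about 0.8 to 2.7 percentage points (90.2% to 91.0% or 92.9%), provided its coefficient may differ by visit. The R² is assumed, and the true value may be smaller. A reader might infer that the trial is underpowered or its primary test unsound; the protocol's own figures show neither.

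**What to change.** In section 9.7.1.6.1 and the matching synopsis text, before unblinding:

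- Add baseline (Visit 2) ADAS-cog14 as a prespecified continuous covariate, with its covariate-by-visit interaction in the MMRM and as a main effect in the imputation ANCOVA.
- Fill a missing baseline value by the overall mean, ignoring treatment arm.
- Treat Screening CDR-SB as optional. Add hippocampal volume only with head-size and scanner adjustment specified.

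The data are already scheduled, so the cost is a sentence or two and about one parameter per visit. If ADAS-cog14 explains nothing further, the loss is those few degrees of freedom out of roughly 930.

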The other continuous secondary efficacy endpoints as defined above will be analyzed using the same MMRM model as the primary efficacy analysis to compare elenbecestat (E2609) 50 mg per day versus placebo on the FAS, using baseline value corresponding to the response variable in the model.

The relationship between clinical changes at 24 months (CDR-SB, ADAS-cog₁₄, MMSE, and FAQ) and changes in each of the biomarkers (amyloid PET, tau PET, CSF A β (1-42), t-tau, p-tau, vMRI, and fMRI) at 24 months, will be evaluated using an ANCOVA model. (revised per Amendments 01, 04, and 05) Changes in clinical scales at 24 months will be the response variables and either continuous or categorical change of biomarkers will be independent variables. The ANCOVA model will also include baseline value for clinical scale as a covariate, randomization stratification variables, treatment group as factors, and other terms as appropriate.

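### If the unstructured and Heterogeneous Toeplitz fits both fail, the fixed fallback order reaches an equal-variance structure before Heterogeneous CS, and the Month 24 standard error could then be too small

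*Protocol*

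**What the plan says.** Protocol Section 9.7.1.6.1 (repeated in the Synopsis) sets the first choice: "An unstructured covariance matrix will be employed to model the covariance of within subject effect". The fallback has a single trigger: "if MMRM fails to converge then a covariance structure with fewer parameters from the following list will be employed". The list is worked through in its stated order until a model converges: "The list of covariance structure will include Heterogeneous Toeplitz, Toeplitz, Heterogeneous Compound Symmetry, and Compound Symmetry". On the data used, "This primary analysis will include all observed post baseline data of the change from baseline in CDR-SB without imputation of missing values".

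Section 9.7.1.6.2 carries the rule further: "The other continuous secondary efficacy endpoints as defined above will be analyzed using the same MMRM model as the primary efficacy analysis".

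The protocol gives the SD of CDR-SB change at 24 months only (Section 9.7.2). It gives no SD at earlier visits and no within-subject correlation, and it does not say whether standard errors are model-based or robust.

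**The concern.** The primary comparison is at Month 24 alone, so its standard error depends on the Month 24 variance. Toeplitz and CS estimate one variance pooled over all visits. If early visits are less variable, the pooled value is too low for Month 24, the confidence interval is too narrow and the p-value too small.

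The protocol gives reasons to expect growth, though no figures. Everyone enters at global CDR 0.5 (Section 9.3.1) and then progresses over 24 months. The secondary slope analysis of the same outcome uses a random coefficient model (Section 9.7.1.6.2), and subject-specific slopes ordinarily imply variance that rises with time.

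Parsimony does not explain the order either. With eight three-monthly visits the parameter counts are 36 (unstructured), 15 (Heterogeneous Toeplitz), 8 (Toeplitz), 9 (Heterogeneous CS) and 2 (CS). Toeplitz therefore precedes a structure that has one more parameter and lets variance differ by visit.

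At stake is the validity of the primary test on that branch. The secondary hierarchy opens only on a significant primary result, so an anticonservative primary test would also open it too easily.

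**Working it through.** **The plan's own figure.** Section 9.7.2 states that the placebo mean and SD "in the placebo group are assumed to be 1.75 and 2.05, respectively", "assuming a 25% reduction in the mean change from baseline CDR-SB at 24 months", 30% dropout, and a calculation "using a 2-sample t-test with 90% power at a significance level of 2-sided alpha =0.05".
- Difference: 0.25 × 1.75 = 0.4375.
- n per arm = 2 × (1.960 + 1.282)² × 2.05² / 0.4375² ≈ 462.
- After dropout: 462 / 0.7 = 660 per arm, 1320 in total, against 1330 stated.
- Power with 665 × 0.7 = 465.5 per arm is 90.2%. The sample size reproduces closely and is not in question.

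**Simple case.** For CS with complete data at Months 3, 6, ..., 24, the ratio of model-based to true SE at Month 24 is

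r = √(mean of the visit variances) / 2.05, and type I error = 2 × (1 − Φ(1.96 r)).

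Example with an assumed Month 3 SD of 0.9 and random-slope growth, v(t) = a + b t²:
- b = (2.05² − 0.9²) / (24² − 3²) = 3.3925 / 567 = 0.00598; a = 0.81 − 9b = 0.756.
- Mean of t² over the eight visits = 229.5, so the mean variance = 0.756 + 0.00598 × 229.5 ≈ 2.129 and the pooled SD = 1.459.
- r = 1.459 / 2.05 = 0.712, and type I error = 16.3%.

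**Wider check.** The simple formula is not exact for Toeplitz, dropout or later visits. The limiting misspecified fit was therefore solved for each structure, with 0% and 30% monotone dropout completely at random. CDR is also scheduled at Visits 14 and 15 (Table 4), so each case was run with and without Months 25 and 27. Every case sets the Month 24 SD to 2.05. The flat and linear-SD cases assume a correlation of 0.97 to the power of the months between visits.

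| Assumed growth (Month 3 SD) | Toeplitz or CS, to Month 24 | Toeplitz or CS, to Month 27 |
|---|---|---|
| None (2.05) | 5.0-6.3% | 5.0-5.8% |
| Linear SD (1.6) | 7.9-10.0% | 7.1-8.5% |
| Linear SD (1.4) | 9.5-12.0% | 8.2-10.0% |
| Linear SD (1.2) | 11.1-14.3% | 9.3-11.5% |
| Linear SD (1.0) | 12.8-16.8% | 10.3-13.1% |
| Linear SD (0.8) | 14.4-19.5% | 11.2-14.7% |
| Random walk (0.98 and 1.18) | 11.0-14.9% | 9.0-12.1% |
| Random slope (0.81 and 1.02) | 14.2-19.7% | 10.4-15.0% |

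Wherever variance grows, r lies between about 0.66 and 0.92 and the type I error between 7.1% and 19.7%. Restricting the Month 3 SD to about 0.8-1.4 gives 8.2-19.7%. Heterogeneous CS, which the plan places after Toeplitz, gives 4.0-7.2% over all these cases.

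**The case against.** The strongest reply is that this branch will rarely be used. The unstructured matrix has 36 parameters for the eight on-treatment visits, against 1330 randomised subjects and about 1330 × 0.7 = 931 Month 24 values. Toeplitz is reached only if the 15-parameter Heterogeneous Toeplitz fails as well, and CS only if Toeplitz and Heterogeneous CS then fail too. As an illustration with an assumed 1% chance of ending on an equal-variance structure, overall type I error would be 0.99 × 5% + 0.01 × (7% to 20%) = 5.02-5.15%. That stands: a reader might infer that the trial's primary type I error is 9-17% or more, and the documents do not support this. The inflation is conditional, and no probability of reaching it is given.

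Two further limits stand. The early-visit SDs and correlations are assumptions, and with flat variance the effect nearly vanishes. The SE estimator is not stated; it may properly be left to the SAP, and a sandwich estimator there would largely remove the problem.

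For the secondary endpoints the risk is smaller still. ADAS-cog₁₄, MMSE and FAQ have four six-monthly on-treatment visits, hence 10 unstructured parameters (21 if both follow-up visits enter), and no inflation was calculated for them.

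What the reply does not answer is the order itself. It is written into the protocol, and it puts a structure that could invalidate the Month 24 test ahead of one that largely protects it.

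**Conclusion.** The point holds as a conditional weakness in a stated rule. If unstructured and Heterogeneous Toeplitz both fail, the next model forces equal variances while Heterogeneous CS is still untried, and the last resort does the same. Given rising variance and model-based standard errors, the type I error on that branch is roughly 7-20%, against 5-6% without variance growth. The direction is the same in every growth scenario tried; the size depends on an SD path that the protocol does not give. The planned unstructured analysis is unaffected.

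**What to change.** Reorder the list in Section 9.7.1.6.1 and the Synopsis: unstructured, Heterogeneous Toeplitz, Heterogeneous CS, and only then any equal-variance structure; or drop Toeplitz and CS. Keeping CS as a final resort is acceptable if the next condition is met: require empirical (sandwich) standard errors whenever the fitted structure is not unstructured. Apply the same rule to the secondary endpoints that use this MMRM. Adding further structures such as ante-dependence is optional.

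The cost is one or two sentences, made before unblinding. Kenward-Roger degrees of freedom are not used with the sandwich estimator, which is negligible with about 931 Month 24 values.
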